**Figure 1: Study Design**

Subjects will be asked to answer a questionnaire regarding adverse effects (Patient reported outcomes version of the common terminology criteria for AEs (PRO-CTCAE)) and medication adherence (PROMIS on medication adherence (Appendices [14.1](#) and [14.2](#)) when they present for the serial blood samples for the pharmacokinetics and pharmacogenomic studies. Additionally, food collection and drug accountability (Appendix [14.3](#)) will be done for the first cycle, prior to pharmacokinetic studies).

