#### **4.3.10 Adverse Event Assessment**

Baseline symptoms at cycle 1 day 1 (prior to initiating therapy) should be detailed and graded. Once treatment has started, AEs will be assessed every 2 weeks during the first cycle. The individual Investigator should record any AE in detail including the date of onset, event diagnosis (if known) or sign/symptom, severity, time course, duration and outcome, relationship of the AE to study drug, and any action(s) taken. AE grade (Based on the CTCAE 5.0) and start date will be documented in the adverse event monitoring form ([Appendix 14.6](#)). Patients will be followed for one cycle.

See section 8 for adverse event monitoring and reporting. The Principal Investigator or sub-Investigators will assess AEs, laboratory data, and vital signs throughout the study. AEs will be assessed by NCI CTCAE Version 5.0. AEs, whether in response to a query, observed by site personnel, or reported spontaneously by the patient will be recorded. All AEs will be followed to a satisfactory conclusion.

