## **6 Study Procedures**

### **6.1 Schedule of Events**

Screening assessments are to be conducted within 28 days prior to initiating protocol therapy unless otherwise specified. CBC with differential and biochemical profile (sodium, potassium, calcium, chloride, bicarbonate, BUN, creatinine, AST, ALT, total bilirubin, albumin, alkaline phosphatase) assessments must be done within 28 days prior to initiating protocol therapy, between day 8-16 of cycle 1, and prior to initiation of cycle 2.

Table 14. Study Calendar: Patients will be followed for one cycle

Study procedure/task	Screening a	Treatment cycle is 28 days	End of study b
Study day	≤ 28 days prior to study entry	Cycle 1 Day 8 - 16	
Procedures			
Eligibility criteria c	X		
Informed consent d	X		
Clinical visits e	X	Per routine clinical practice	
Adverse Events		X	X
CYP3A5 Screening f	X		
Treatments g			
Ribociclib		600 mg PO once daily for 21 days, followed by a 7-day rest period to complete a 28-day treatment cycle	
Fulvestrant		500 mg IM injection on days 1 and 15	
Letrozole		2.5 mg PO daily	
Goserelin		3.6 mg SQ every 28 days or 10.8 mg SQ every 12 weeks	
Leuprolide depot		3.75 mg IM every 28 days or 11.25 mg IM every 12 weeks	
Tests			
Blood draw for pharmacogenomic studies		X	
Serial blood draws for pharmacokinetic studies			

 
Immediately prior to the ribociclib dose, and 0.5hr ± 5min, 1hr ± 5min, 2hr ± 15min, 4hr ± 15min, 6hr ± 15min after the daily dose of ribociclib.
 
		X	
Electrocardiogram h	X	X	X
CBC with differential and CMP i	X	X	X
Pregnancy Test j	X		
NCI CTCAE PRO questionnaire k	X	X	X
Adverse event monitoring log	X	X	X
Medication adherence PROMIS questionnaire and drug accountability		X	X

a Screening: All assessments should be performed within 28 days prior to study entry. Study entry will be defined by confirmation of eligibility.

b This visit will occur prior to initiation of cycle 2 (e.g., 29th day of the study, plus or minus 3 days)

c Eligibility Criteria Evaluation: Patients must meet all of the eligibility criteria reported in the protocol

d Informed Consent: Must be obtained prior to undergoing any study-specific procedures.

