e Clinical Visits: clinical visits will include medical history, vital signs and physical exam and will be conducted as per local practice and as clinically indicated. Physical Examination includes a general clinical examination of major body systems.

f To be performed after informed consent and used for screening according to sections 3.6 and 4.3.7. CYP3A5 Screening may be bypassed per Principal Investigator discretion if the necessary number of participants with each phenotype are enrolled (cohort of AA or Black participants - at least 3 poor metabolizers; cohort of NHW participants - at least 3 intermediate or normal metabolizers). If CYP3A5 is already performed it does not need to be repeated within the window of  $\leq$  28 days.

g All patients will receive ribociclib plus physician choice endocrine therapy with fulvestrant or letrozole. Luteinizing hormone-releasing hormone (LHRH) agonist (goserelin or leuprolide) will be required for premenopausal women.

h To be performed at these times per routine clinical practice and the treating physician: prior to treatment initiation; repeat on day 8-16 of cycle 1, and prior to initiation of cycle 2

i To be performed at these times per routine clinical practice and the treating physician: baseline, repeat on day 8-16 of cycle 1, and prior to initiation of cycle 2

j To be performed at these times per routine clinical practice and the treating physician: Pregnancy test (serum or urine), required for women of childbearing potential

k Questionnaires to be completed within 28 days of C1D1

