## 9.2 Statistical Analysis Plan

Primary analyses will be performed as follows. Within each race-based cohort, the ribociclib exposure which measured by ribociclib AUC will be summarized by median [Interquartile range, IQR], and two-sample t-test if normality holds or Wilcoxon-Mann-Whitney test will be used to compare AUC between CYP3A5 poor metabolizers and CYP3A5 intermediate or normal metabolizer in each independent race-based cohort. Secondary analyses will be performed as follows. Descriptive statistics will be used to characterize the data profile, frequency and percentages for categorical variables, and mean (SD) or median [IQR] for continuous variables based on the data normalization. Multiple regression will be used to identify variables associated with ribociclib AUC. To best account for any factor that may affect ribociclib exposure, covariates to be assessed include CYP3A5 metabolism status, renal function, liver function, age, race, weight, sex, among others. Any covariates with  $P < 0.2$  on univariate analysis will enter the stepwise multiple linear regression model, with  $P < 0.05$  considered statistically significant. This methodology will also be used to assess a change in absolute neutrophil count and QTc as the outcome variable. Depending on data distribution, a two-sample t-test or Wilcoxon-Mann-Whitney test will be used for 1) a change (baseline and C1D8-C1D16) in continuous variables (e.g., QTc, absolute neutrophil count) between CYP3A5 poor metabolizers and CYP3A5 intermediate or normal metabolizers, 2) to check the association between a continuous variables and categorical risk factors. Pearson correlation coefficient or Spearman correlation coefficient will be calculated to measure the association between two continuous variables. Fisher's exact test will be used for checking the association between two categorical variables. AEs will be assessed with descriptive statistics and univariate logistic regression will assess the occurrence of specific AEs with pharmacokinetic properties (e.g., AUC,  $C_{max}$ ). The approach from the linear regressions will be adapted to logistic regression to identify covariates associated with the occurrence of grade III or IV neutropenia.

Descriptive analysis of the PRO-CTCAE adverse event log to determine frequency of adverse events by race and by CYP3A5 genotype.

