Descriptive statistics will be used to describe the patients reported outcomes in the survey (see Appendices). As an exploratory analysis, multiple regressions will be used to assess the relationship between patients reported outcomes and other covariates (mentioned above) with ribociclib AUC.

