## 14.2 Patient Reported Outcomes of CTCAE

### NCI PRO-CTCAE™ ITEMS

Item Library Version 1.0

English

Form Created on 05 August 2020

As individuals go through treatment for their cancer, they sometimes experience different symptoms and side effects. For each question, please select the one response that best describes your experiences over the past 7 days...

1a. In the last 7 days, what was the SEVERITY of your MOUTH OR THROAT SORES at their WORST?				
 None	 Mild	 Moderate	 Severe	 Very severe

1b. In the last 7 days, how much did MOUTH OR THROAT SORES INTERFERE with your usual or daily activities?				
 Not at all	 A little bit	 Somewhat	 Quite a bit	 Very much

2a. In the last 7 days, how OFTEN did you have NAUSEA?				
 Never	 Rarely	 Occasionally	 Frequently	 Almost constantly

2b. In the last 7 days, what was the SEVERITY of your NAUSEA at its WORST?				
 None	 Mild	 Moderate	 Severe	 Very severe

3a. In the last 7 days, how OFTEN did you have VOMITING?				
 Never	 Rarely	 Occasionally	 Frequently	 Almost constantly

3b. In the last 7 days, what was the SEVERITY of your VOMITING at its WORST?				
 None	 Mild	 Moderate	 Severe	 Very severe

**4a.** In the last 7 days, how OFTEN did you have BLOATING OF THE ABDOMEN (BELLY)?

 Never	 Rarely	 Occasionally	 Frequently	 Almost constantly
-----------------------------	------------------------------	------------------------------------	----------------------------------	---

**4b.** In the last 7 days, what was the SEVERITY of your BLOATING OF THE ABDOMEN (BELLY) at its WORST?

 None	 Mild	 Moderate	 Severe	 Very severe

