## 14.6 Adverse event monitoring log (CTCAE 5.0):

Adverse event	Grade 1	Grade 2	Grade 3	Grade 4	Baseline	Mid-cycle visit	End of study
						Mark N/A or grade for each visit AND date of onset	
Rash	<10% BSA	10-30% BSA	Severe rash, >30%, SJS	Any %, requiring antibiotics, TEN			
Interstitial Lung Disease/ Pneumonitis	Asymptomatic	Symptomatic	Severe Symptomatic	Life threatening			
Nausea	Loss of appetite without alteration of eating habits	Oral intake decreased without weight loss, dehydration, malnutrition	Inadequate oral intake, hospitalization indicated	N/A			
Vomiting	Intervention not indicated	Outpatient IV hydration	Tube feeding, TPN, hospitalization	Life threatening			
Diarrhea	Increase of <4 stools per day	Increase of 4-6 stools per day	>7 stools per day over baseline	Life threatening			
Constipation	Occasional or intermittent symptoms; occasional use of stool softeners, laxatives, dietary modification, or enema	Persistent symptoms with regular use of laxatives or enemas	Obstipation with manual evacuation indicated; limiting self-care ADL	Life threatening			
Fatigue	Relived by rest	Not relieved by rest, limiting basic activities of daily living	Limiting self-care	N/A			
Anorexia	Loss of appetite without alteration in eating habits	Oral intake altered without significant weight loss or malnutrition; oral nutritional supplements indicated	Associated with significant weight loss or malnutrition (e.g., inadequate oral caloric and/or fluid intake); tube feeding or TPN indicated	Life-threatening consequences; urgent intervention indicated			

Alopecia	<50% of normal, only obvious to close inspection	>50% of normal, a wig or hair piece is necessary; psychosocial impact	N/A	N/A			
Arthralgia	Mild pain	Moderate pain, limiting activities of daily living	Severe pain, limiting self-care	N/A			
Headache	Mild pain	Moderate pain, limiting activities of daily living	Severe pain, limiting self-care	N/A			
Hot flush *	Mild	Moderate, limiting activities of daily living	Severe	N/A			
Other							
Other							
Other							

Abbreviations: LLN: lower limit of normal; ULN: upper limit of normal; BSA: body surface area

\*No CTCAE

Baseline visit → Completed by \_\_\_\_\_ Date: \_\_\_\_\_  
 Mid-cycle 1 visit → Completed by \_\_\_\_\_ Date: \_\_\_\_\_  
 End of study visit → Completed by \_\_\_\_\_ Date: \_\_\_\_\_

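### Section 9.2 tabulates PRO-CTCAE adverse events by race and CYP3A5 genotype without using the scheduled screening questionnaire, so pre-existing symptoms may be counted as events

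*Combined protocol and SAP*

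**What the plan says.** Section 9.2 describes the analysis in one sentence: "Descriptive analysis of the PRO-CTCAE adverse event log to determine frequency of adverse events by race and by CYP3A5 genotype". It names no visit, no score threshold and no baseline rule. The next paragraph adds descriptive statistics for the patient-reported survey and an exploratory regression involving ribociclib AUC, again without mentioning baseline. For QTc and absolute neutrophil count, the same section does specify change from baseline to C1D8-C1D16.

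In Table 14 (section 6.1) the row "NCI CTCAE PRO questionnaire" is marked at screening, at cycle 1 day 8-16 and at end of study. Its footnote k reads "Questionnaires to be completed within 28 days of C1D1". The text under Figure 1 in section 4.1 places the questionnaire at one visit only, "when they present for the serial blood samples for the pharmacokinetics and pharmacogenomic studies".

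The questionnaire in Appendix 14.2 tells the patient: "please select the one response that best describes your experiences over the past 7 days".

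Clinician-assessed events are handled separately. Section 4.3.10 says "Baseline symptoms at cycle 1 day 1 (prior to initiating therapy) should be detailed and graded". The CTCAE 5.0 monitoring log in Appendix 14.6 has Baseline, Mid-cycle and End of study columns with the instruction "Mark N/A or grade for each visit AND date of onset".

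**The concern.** A PRO-CTCAE answer reports how often a symptom occurred or how bad it was in the last week. It does not say whether the symptom began after treatment started. Without the screening answer, a post-baseline response measures prevalence. Calling it an adverse event attributes to treatment whatever the patient already had.

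The protocol expects such symptoms:

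- Section 3.4 admits patients with residual grade 1 toxicity from earlier therapy. It exempts alopecia, neuropathy and other toxicities judged not to be a safety risk from that limit. Hair loss is item 10a of the questionnaire.
- Section 3.3 allows ECOG performance status 0-3.
- Section 4.3.2 collects symptoms of the malignancy at screening.

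What is at stake is the comparison between groups. Toxicity by race cohort is secondary objective 1, and the correlation of PRO-CTCAE toxicities with pharmacokinetics is an exploratory endpoint in section 2.5. If prior treatment or disease burden differs between groups, an unadjusted table can show a race or genotype difference that was there before the first dose.

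**Working it through.** The plan gives no figure for this analysis, so there is nothing to reproduce. The check has two parts.

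**1. The text.**

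- Is a pre-treatment measure planned? Yes, in the screening column of Table 14.
- Can the instrument separate new from old symptoms without it? No. Appendix 14.2 has a 7-day recall and no onset question.
- Does section 9.2 say how the screening score enters? No. It mentions neither change from baseline, nor worst score above baseline, nor exclusion of symptoms already present.
- Does section 9.2 use baseline elsewhere? Yes, for QTc and absolute neutrophil count.

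**2. Illustration.** All inputs here are assumptions. Let b be the proportion with the symptom at screening, all of whom still have it after baseline. Let e be the probability of a new symptom among those without it at screening.

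Frequency if any post-baseline symptom counts: F = b + (1 - b)e.

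Difference between two groups with the same e: (b2 - b1)(1 - e).

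With e = 30% in both groups and b1 = 20% in the first, F1 = 0.20 + 0.80 × 0.30 = 44%. For the second group:

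| b2 | F2 | F2 - F1 |
|---|---|---|
| 30% | 0.30 + 0.70 × 0.30 = 51% | 7 points |
| 40% | 0.40 + 0.60 × 0.30 = 58% | 14 points |
| 50% | 0.50 + 0.50 × 0.30 = 65% | 21 points |

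The risk of a new symptom is identical throughout, so the whole 7-21 points comes from baseline.

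**What a baseline-adjusted rule would report.** If an event is a worst post-baseline score above the screening score, worsening counts as well as new onset. Let w be the probability of worsening among those symptomatic at screening. The frequency is then bw + (1 - b)e.

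- If w = e = 30%, it is 30% in both groups whatever b is, and the artefact disappears.
- If w = 0, the first group has 0.80 × 0.30 = 24% and the second 0.70 × 0.30 = 21% down to 0.50 × 0.30 = 15%. That is a gap of 3-9 points in the other direction, because patients with the symptom at screening can no longer contribute an event.

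The adjusted count is therefore the better summary, but it should be read beside the raw screening and post-baseline frequencies.

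**The case against.** The strongest objection is that the SAP is silent and has not made a wrong choice. A reader might infer that it discards the screening scores and counts existing symptoms as events. The text does not say so, and a by-visit table that includes screening would also fit the sentence. This stands: the point is that such counting may happen, not that it is planned.

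Second, the sentence may refer to another instrument. The only adverse event log in the documents is Appendix 14.6, which has a Baseline column and onset dates, and the survey gets its own sentence afterwards. Section 4.3.10 requires baseline grading, and section 8.2 starts adverse event recording on the CRF at the first ribociclib dose. The ambiguity is real, but it does not close the gap. Appendix 14.6 is a CTCAE 5.0 log, not PRO-CTCAE, and has no named rows for mouth sores, bloating, limb swelling, palpitations, aching muscles or vaginal dryness, all of which Appendix 14.2 asks about. The section 8.2 window governs CRF events, not questionnaire answers. Section 9.2 gives no baseline rule for either form.

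Third, a reader might infer that one pre-existing symptom moves a rate by 33 points, since the smaller phenotype group may have only 3 patients in a cohort. Section 9.2 asks for frequencies by race and by genotype, not crossed. By race the table is 18 versus 18. By phenotype across cohorts, at the section 3.3 quotas, it is 3 + 15 = 18 versus 18. A group of 3 arises only if race and phenotype are crossed, and one patient in 3 is 33 points for any event.

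Finally, the analysis is descriptive, has no test attached, and is neither the primary endpoint nor a listed secondary endpoint. That stands, and it limits the importance of the point.

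**Conclusion.** The point holds as an inexpensive improvement. Section 9.2 gives no role to a screening questionnaire that Table 14 schedules, and the instrument cannot distinguish new symptoms from old ones without it. Pre-existing symptoms may be counted as events, and baseline differences may be read as toxicity differences by race or genotype.

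The size is unknown because the documents give no baseline prevalence. The 7-21 points rest on an assumed 30% new-onset risk in both groups, assumed baseline prevalences of 20% versus 30-50%, full persistence of baseline symptoms, and counting any post-baseline symptom as an event. Less persistence or a smaller baseline imbalance would shrink the gap, and equal baselines would remove it. The primary comparison of ribociclib AUC is unaffected.

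**What to change.** In section 9.2:

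- Name the instrument: the Appendix 14.2 questionnaire or the Appendix 14.6 log.
- Count a PRO-CTCAE event when the worst post-baseline score exceeds the screening score, so that both new onset and worsening count. State how this works for items with several attributes and for the yes/no rash item, which cannot worsen.
- Show raw screening and post-baseline frequencies alongside, by race and by phenotype, with the number of patients who have a screening form in each group.

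Elsewhere, reconcile the text under Figure 1 in section 4.1 (pharmacokinetic visit only) with Table 14 (three time points). State in footnote k that the screening form is completed before the first ribociclib dose.

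The cost is wording in the SAP and two clarifications in the protocol. No new assessment is needed, because Table 14 already schedules the screening form. If a site followed the section 4.1 text instead, some screening forms may be missing, which is a further reason to report that denominator.

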## 9.3 Correlative Studies

The PharmacoScan™ microarray provides data on 4627 markers for each patient. These data serve as a rich opportunity for hypothesis-generating correlative studies with pharmacokinetic properties or AEs. Study designs for exploratory pharmacogenomics are usually conducted as either candidate gene studies or a genome-wide association study (GWAS) (37). This work will be conducted as a candidate gene analysis as the sample size ( $n = 36$ ) is too limited to attempt a study similar to a GWAS.

Candidate genes will be selected based on biological plausibility. For example, although data around *CYP3A4* are limited (section 1.4), it is a prime candidate gene given overlapping substrate specificity with *CYP3A5* and the significant sequence homology (approximately 84%) between *CYP3A4* and *CYP3A5*. Additional candidate genes will be identified based on metabolic pathways, signaling pathways, ribociclib mechanism of action.

A list of genes will be created through a primary literature review and information from the FDA review. Given the pace of discovery work in this field, the list will be generated at or near the completion of the data collection. Prior to the analysis, genes will be ranked so that the stronger candidates are tested with a given outcome first. For example, *CYP3A4* will likely be the first gene assessed for an association with ribociclib AUC with statistical analysis as described in section 9.3 and those similar to other work (38).

Another example of a candidate gene is the *ABCB1* gene which is included in the PharmacoScan™ assay and single nucleotide variations were recently associated with persistent chemotherapy induced alopecia (39). A recent study in our institution showed that the use of scalp cooling in African American/Black women with early stage breast cancer receiving chemotherapy was not effective preventing alopecia; alopecia was prevented in 0/11 patients while previous studies in White populations have reported 50-80% success (40). For this exploratory analysis we aim to assess if this difference could be related to genetic variations and this could potentially be studied in the future with cytotoxic agents associated to alopecia. Depending on how many genes are in the list, we will provide the q-value as well to control the false discovery rate and we may also attempt a learning algorithm such as LASSO or a variant of it to further screen the associated markers

## 9.4 Safety Analysis

Safety data will be summarized for all patients who received one cycle of ribociclib.

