### **3.6.2 Safety and Tolerability**

Any patient who received ribociclib and undergoes complete pharmacokinetic and pharmacogenomic studies will be valuable for safety and tolerability as measured by NCI CTCAE v5.0.

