#### **4.3.12 Discontinuation of Individual Patients**

When a patient discontinues the study treatment (without reaching a protocol-defined endpoint), the investigator will notify the Principal Investigator as soon as possible (provided, in each case, patient care and safety are not compromised). When a patient discontinues the study treatment, a final visit will be conducted, preferably prior to the initiation of another anticancer therapy. However, these procedures should not interfere with the initiation of any new treatments or therapeutic modalities that the investigator or patient's treating physician feel is necessary to treat the patient's condition. Following discontinuation of the study drug, the patient will be treated in accordance with the investigator's/treating physician's best clinical judgment.

At the final visit, the reason(s) for the discontinuation from the study will be recorded and a physical examination, body weight, vital signs measurement, laboratory analyses, performance status, tumor assessment, and an assessment of AEs will be performed as soon as possible after discontinuation from the study treatment. If a patient is discontinued from the study with an ongoing AE or an unresolved clinically significant laboratory result, the site will attempt to provide follow up until a satisfactory clinical resolution of the laboratory result or AE is achieved.

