#### **4.3.13 Patient Replacement Criteria**

If a patient is enrolled but is unable to tolerate ribociclib or to participate in laboratory workup and cardiac studies as well during cycle 1, she would be deemed non-evaluable. In the case of an unexpected trauma or death that is considered unrelated to the underlying solid tumor malignancy, patient would be deemed to be non-evaluable.

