### **5.3.1 Ribociclib**

Commercially available Ribociclib 600 mg (3 x 200 mg tablets by mouth) QD on days 1 to 21 of a 28-day cycle, followed by 7 days off ribociclib (Days 22 to 28).

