### **8.2 Reporting Period**

For SAEs, the active reporting period to the principal investigator begins from the time that the patient provides informed consent, which is obtained prior to the patient's participation in the study, through the completion of cycle 1.

AEs (serious and non-serious) should be recorded on the CRF from the time the patient has taken at least one dose of ribociclib through the last patient visit.

Death must be reported if it occurs during the SAE reporting period after the last dose of ribociclib, irrespective of any intervening treatment.

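### On its plain reading, Section 9.4 leaves early toxicity stops out of the safety summary, and it does not agree with Section 3.6.2

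*Combined protocol and SAP*

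**What the plan says.** Four parts of the combined protocol and SAP bear on who counts for safety.

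- Section 9.4 is a single sentence: "Safety data will be summarized for all patients who received one cycle of ribociclib". It does not say whether this means completing the cycle or starting it.
- Section 5.3.1 gives the cycle as ribociclib "QD on days 1 to 21 of a 28-day cycle, followed by 7 days off ribociclib".
- Section 3.6.2 uses another criterion: "Any patient who received ribociclib and undergoes complete pharmacokinetic and pharmacogenomic studies will be valuable for safety and tolerability". The word valuable there is presumably evaluable. Sections 4.1 and 4.3.8 place the sampling between days 8 and 16 of cycle 1.
- Section 4.3.13, headed as replacement criteria, says who is non-evaluable: "If a patient is enrolled but is unable to tolerate ribociclib or to participate in laboratory workup and cardiac studies" during cycle 1, and also cases of unrelated trauma or death. It does not name the analysis affected or say that a replacement follows.

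Section 9.2 describes the AE analyses, including a descriptive one "to determine frequency of adverse events by race and by CYP3A5 genotype", and names no analysis population. No section defines a set of all patients who took at least one dose.

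Data collection is wider than the summary. Section 8.2 says "AEs (serious and non-serious) should be recorded on the CRF from the time the patient has taken at least one dose of ribociclib". Section 4.3.12 adds that, at a final visit, "an assessment of AEs will be performed as soon as possible after discontinuation from the study treatment". Section 3.5 keeps patients who stop treatment enrolled so that later outcomes can be collected.

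**The concern.** A safety summary limited to patients who got through the dosing period is selected on the outcome it describes. A patient who has to stop in cycle 1 leaves both the numerator and the denominator, and she is among the most informative patients for tolerability.

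The protocol foresees such stops. Table 7 requires permanent discontinuation for QTcF prolongation with signs of serious arrhythmia. Table 8 requires discontinuation for raised AST or ALT together with raised bilirubin. The ECG and laboratory tests on days 8 to 16 can reveal either one while dosing is still under way. Comparing toxicity between the race cohorts is a secondary objective (Section 2.3), and each cohort has only 18 patients, so one omitted case is visible in a table.

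**Working it through.** The plan gives no figure to reproduce. The check compares set membership and then sizes the loss.

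**Membership by case**

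| Case | Section 9.4, plain reading | Section 3.6.2 |
|---|---|---|
| Permanent stop before complete PK/PGx sampling | Out | Not covered |
| Permanent stop after complete PK/PGx sampling, before dosing ends on day 21 | Out | In |
| Full dosing, PK/PGx incomplete | In | Not mentioned |
| Full dosing, PK/PGx complete, stop decided at the visit before cycle 2 | In | In |

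The second row is the firm conflict. The first row shows that adopting Section 3.6.2 in place of 9.4 would not be a full cure. The last row limits the problem. Table 14 says of the end-of-study visit that "This visit will occur prior to initiation of cycle 2", at day 29 plus or minus 3. Its earliest day is 29 − 3 = 26, after dosing has ended on day 21.

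**Expected number lost**

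Inputs are n = 36 (Section 3.2.2) and an assumed probability q of a permanent toxicity stop during days 1 to 21. The documents give no q, so a range is shown. The expected number is 36q, and the chance of at least one is 1 − (1 − q)^36.

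| Assumed q | Expected patients | Chance of at least one |
|---|---|---|
| 0.5% | 36 × 0.005 = 0.18 | 1 − 0.995^36 = 0.165 |
| 1% | 36 × 0.01 = 0.36 | 1 − 0.99^36 = 0.304 |
| 2% | 36 × 0.02 = 0.72 | 1 − 0.98^36 = 0.517 |

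Table 3 gives discontinuation of ribociclib for AEs as 3% to 9% in the three pivotal trials. That covers all of their treatment time, so 36 × 0.03 = 1.1 to 36 × 0.09 = 3.2 patients is a ceiling for cycle 1 and not an estimate.

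**Effect of one stop**

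Suppose toxicity discontinuations are tabulated on the 9.4 set and the patient is not replaced. The 95% intervals are Clopper-Pearson.

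- Overall: 1/36 = 2.8% (0.1% to 14.5%) becomes 0/35 = 0% (0% to 10.0%).
- In her race cohort: 1/18 = 5.6% (0.1% to 27.3%) becomes 0/17 = 0% (0% to 19.5%).

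The direction is fixed. Removing one patient who had the event turns x/n into (x − 1)/(n − 1), which is smaller whenever x < n. If she is replaced, the denominator is restored but the event is still missing.

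**The case against.** The strongest reply is that Section 9.4 speaks of receiving a cycle, not completing one. Each patient is followed for one cycle only, so the sentence may loosely mean everyone treated in the study. That reading is possible. Exclusion is the more literal reading once Section 5.3.1 has set the length of a cycle, but the term is not defined, so the exclusion rests on plain reading. If the looser meaning is intended, Section 9.4 should say so.

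Several stronger readings are tempting, and the documents do not support them.

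- A reader might infer that safety data are lost. They are not: AEs are recorded from the first dose, patients who stop have a final AE assessment, and serious AEs go to the Data and Safety Monitoring Committee (Section 9.5).
- A reader might infer that the AE, QTc and neutrophil analyses are all affected. Section 9.2 carries no one-cycle restriction, so they are affected only if the 9.4 set is used there.
- A reader might infer that Sections 9.4 and 3.6.2 contradict each other in both directions. Section 3.6.2 states a sufficient condition. It is silent on a fully dosed patient with incomplete PK sampling and does not exclude her.
- A reader might infer that non-evaluable is undefined. Section 4.3.13 lists who it covers; only the consequence is unstated.
- A reader might apply the 3% to 9% rates to cycle 1. They are whole-trial rates.

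It also stands that the expected loss is below one patient at every assumed rate from 0.5% to 2%.

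**Conclusion.** The point holds, and it is minor. On the plain reading, the safety summary selects on tolerating the first cycle. That conflicts with Section 3.6.2 for a patient who stops after complete PK/PGx sampling and before day 21. A stop before that sampling is placed by neither section, and Section 4.3.13 does not settle which analysis its label governs.

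The size rests on assumed stop rates: 0.2 to 0.7 of 36 patients at 0.5% to 2%, with a 17% to 52% chance of at least one. The number is small, but the error in the rate of toxicity stops runs one way, towards better apparent tolerability. The 1/36 to 0/35 illustration further assumes that discontinuations are tabulated on the 9.4 set without replacement. The effect is confined to the 9.4 summary unless that set is carried into Section 9.2. No bias in the primary AUC comparison follows from this point.

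**What to change.** - In Sections 9.4 and 3.6.2, define one safety set: every patient who took at least one dose of ribociclib, with events counted up to stopping or the end of study.
- In Section 9.2, name this set for the AE analyses.
- In Section 4.3.13, state that non-evaluable governs PK evaluability and replacement, not safety, and say whether such a patient is replaced.

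A separate table of cycle 1 toxicity discontinuations by cohort and CYP3A5 phenotype is optional, given an expected count below one.

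The cost is a sentence in each of Sections 9.4, 3.6.2 and 4.3.13 and a line in 9.2. No new data are needed and no clinical rule changes. The downside is that the safety set will include some patients with partial exposure, which can be handled by reporting the number of doses taken.
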